**Methods/Randomization:** At study entry all participants will complete the Hospital Anxiety and Depression Scale (HADS). The HADS is a 14-item screening scale developed to indicate the possible presence of anxiety and depression . HADS consists of a 7-item anxiety subscale and a 7-item depression subscale. A score of > 8 identifies a positive history of anxiety or

depression symptoms . The validity of the HADS has been extensively studied in a variety of populations including the general population, general practice and psychiatric patients. In our previous analyses of ICU nurses, the HADS Cronbach's alpha was 0.86 3, 8. In order to complete Aim 2.2 and due to our staffing capacity, we will conduct one treatment and one control group in each 16 hour intervention period. We will recruit ~24 nurses at a time, who will be randomized on a 1:1 basis to either treatment (n=12) or control (n=12). Therefore at least 10 months will be required to complete the pilot study (5 treatment and 5 control cohorts x 2 month interventions = 10 months).

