#### **B. Description of Population to be Enrolled:**

We will enroll ICU nurses from four Colorado hospitals. From the beginning of our proposal preparation, all of the Chief Nursing Officers (CNOs) and ICU Nurse Managers have been involved in the study development. Uniformly, these CNOs are excited to have nurses from their hospital participate in the trial. Enrollment at diverse hospitals will help substantiate the generalizability of our findings. There are no studies at these hospitals that compete with this study enrollment.

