### **F. Data Analysis Plan:**

**Quantitative Statistical Analysis and Power Analysis:** For Aim #2.1, our primary outcome variable will be the post-pre change in CD-RISC scores in intervention and control subjects. Previous studies suggest that clinically significant changes in CD-RISC scores range from 12-19 points with an approximate standard deviation of 20 points. With a total enrollment of 160 subjects, we will be able to detect a difference of 12 points in CD-RISC score between the control and intervention groups with 90% power (assuming a 2-sided significance level (alpha) of 0.05 and an equal variance *t* test; software: PASS 13); we will be able to detect a difference of 19 points in CD-RISC score between the control and intervention groups with 100% power. We will also examine the change in MBI, PDS, and HADS scores in both the treatment and control groups. We will corroborate our comparisons of changes in all scores using robust bootstrap and permutation methods. When measuring constructs involving psychological mood, there is always concern that the answers reflect transient, less stable responses. The participant responses may simply change over time making certain paired analyses difficult to interpret. Therefore, we will calculate a coefficient alpha to estimate measurement reliability.

If we fail to find a bigger increase in CD-RISC score in the intervention group, as we expect, that may be due to interactions (contamination) between members of the intervention and control groups. We will assess the extent of contamination in Aim #2.2, for which our primary outcome variable will be the change in mean baseline CD-RISC score over time within each ICU. If there is, on average, greater than 30% contamination (that is, if baseline pre-enrollment CD-RISC scores increase), we will consider using a randomized cluster design for the subsequent multi-center clinical trial. If baseline CD-RISC scores increase 4 points over each intervention period, we will be able to detect that progressive increase with roughly 92% power (10,000 simulations using the Jonckheere-Terpstra ordered alternatives procedure; software: R). Our assessment of changes in baseline CD-RISC scores over time will consider the point and interval estimates of the changes in addition to formal statistical significance which may be of less use in this setting. All analyses will use SAS 9.3 and  $p < 0.05$  will be considered significant.

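### No stratification by hospital is specified and the primary comparison has no hospital term, a small loss of precision that is cheap to avoid

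*Combined protocol and SAP*

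**What the plan says.** The Methods/Randomization paragraph of section IV holds the only description of allocation. "We will recruit ~24 nurses at a time", it says, "who will be randomized on a 1:1 basis to either treatment (n=12) or control (n=12". One treatment and one control group run in each period, and the duration is worked out as "5 treatment and 5 control cohorts x 2 month interventions = 10 months", which gives five rounds.

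Section B states: "We will enroll ICU nurses from four Colorado hospitals". It does not say how many nurses each hospital supplies, or whether every round draws on all four.

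Section F bases power for the primary outcome on an equal-variance t test, corroborated by bootstrap and permutation methods. Hospital does not appear in that comparison. The unit is used only for Aim 2.2, whose outcome is the "change in mean baseline CD-RISC score over time within each ICU". Stratification, blocking within hospital, minimisation and the way assignments are generated are not mentioned anywhere.

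**The concern.** A 12/12 split of a round fixes the arm totals but not the split within any hospital. Staffing, management and workload differ between hospitals and could plausibly affect how much a nurse's CD-RISC score changes. If they do, leaving the hospital mix of each arm to chance adds variance that the design could remove, and a t test without a hospital term leaves that variance in the error. The permutation check is also promised without saying that it will follow the allocation actually used. At stake are the precision of the primary contrast and the match between analysis and design, not validity.

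**Working it through.** **Inputs from the documents.** Four hospitals (section B). Rounds of about 24 split 12/12, five rounds, so 5 × 24 = 120 nurses (section IV). Difference 12, SD 20, two-sided alpha 0.05, t test, 160 subjects, stated power 90% (section F).

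**Assumptions, because the documents give neither figure.** Six nurses per hospital per round. Hospital explains a share r of the variance in CD-RISC change, with r from 0 to 0.10.

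**1. The plan's own power figure.** With 80 per arm, SE = 20 × √(2/80) = 3.162 and the noncentral t gives 96.5%, not the stated 90%. With 60 per arm, SE = 20 × √(2/60) = 3.651 and power is 90.3%. The stated 90% therefore fits the 120 nurses of the five rounds and not 160. That conflict is a separate matter. The steps below use 120, and 160 is noted where it matters.

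**2. Imbalance within a round.** The number treated among a hospital's 6 nurses is hypergeometric (24, 6, 12).

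P(5:1 or worse) = 2 × [C(18,12) + 6 × C(18,11)] / C(24,12) = 2 × (18,564 + 6 × 31,824) / 2,704,156 = 0.155.

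**3. Imbalance over five rounds.** Variance per round = 12 × (6/24) × (18/24) × (12/23) = 1.174. Over five rounds it is 5.87, so the SD is 2.42. The treated total per hospital is 15 ± 2.4 of 30.

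**4. What stratifying alone adds once hospital is in the model.** Treatment information is the sum over hospitals of n₁n₀/n. Evenly split: 4 × (15 × 15/30) = 30. Left to chance, the expected value is 4 × (225 − 5.87)/30 = 29.22. The SE ratio is √(30/29.22) = 1.013, so stratifying narrows the SE by about 1.3% whatever r is.

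**5. What stratifying and adjusting give together.** The SE falls from 3.651 to 3.651 × √(1 − r). Power is for 12 points with 120 nurses. The adjusted columns have 120 − 9 = 111 degrees of freedom (intercept, treatment, three hospital and four round terms), and the adjusted-only column uses the SE times 1.013.

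| r | t test, no stratification | hospital and round terms only | stratified, with both terms |
|---|---|---|---|
| 0 | 90.3% | 89.5% | 90.3% |
| 0.02 | 90.3% | 90.1% | 90.8% |
| 0.05 | 90.3% | 91.0% | 91.7% |
| 0.10 | 90.3% | 92.3% | 93.0% |

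The combined gain is 0 to about 3 points. At r = 0.10 adjustment alone supplies about 2.0 of the 2.7 points. At r = 0.05 it supplies about half. At r = 0.02 it supplies none, but the whole gain is then half a point. With 160 nurses the gain at r = 0.10 is smaller still: SE = 3.162 × √0.90 = 3.00 and power goes from 96.5% to 97.8%.

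**6. Validity.** In simulated trials with no treatment effect (five rounds of 24, six per hospital, no stratification, plain t test), the rejection rate stayed at about 5% for r of 0, 0.05 and 0.10. Stratifying and then omitting hospital from the model makes the test conservative: at r = 0.10 the effective cut-off is 1.980/√0.90 = 2.087, a two-sided level of about 4%. Stratification and the hospital term should therefore go in together.

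**The case against.** The case against is strong on size and on how much the text supports.

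- A reader might infer that the allocation is known to be simple and unstratified. The documents are silent. They support only the statement that no stratification by hospital is specified.
- The imbalance figures need rounds that mix the hospitals. If a round came from one hospital, the 12/12 split would balance it automatically.
- No hospital variance in CD-RISC change is given, and a post-pre change already removes stable differences in level between hospitals. The share r may be near zero, and the gain with it.
- A reader might be struck that, on the six-per-hospital assumption, at least one of the four hospitals splits 5:1 or worse in 43% of rounds. The primary comparison pools rounds, so step 3 is the relevant figure.
- A reader might infer that stratifying would materially clarify the contamination question of Aim 2.2. It would not. The number of trained nurses in a unit depends mainly on how many enrol from it: a hospital supplying 12 would have 6 trained, and one supplying 3 would have 1 or 2. Balancing arms within hospital does not reduce contamination either.
- Nor is the change free of cost, because odd hospital counts have to be reconciled with 12/12.

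All of this stands. It reduces the point to a minor improvement but does not remove it: the silence on hospital is in the text, and the remedy is small.

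**Conclusion.** The point holds as a cheap improvement, not as an error. The plan specifies no balance by hospital at allocation and no hospital term in the primary comparison. There is no bias and no inflation of type I error. The avoidable loss is about 0 to 3 power points at 120 nurses for an assumed hospital share of 0 to 10% of the variance, and stratification itself contributes about 1% in SE. These sizes rest on the assumed even mix of six nurses per hospital per round and on the assumed variance share. Nothing in the pilot's stated decisions turns on a loss of this size.

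**What to change.** In the Methods/Randomization paragraph of section IV, state how assignments are generated and add wording such as: 'Within each round, nurses are allocated 1:1 stratified by hospital; where a hospital contributes an odd number, the extra nurse is assigned at random so that the arms stay as close to 12/12 as possible.' In section F, include hospital and round as fixed effects in the primary comparison, and carry out the permutation check by permuting within round and hospital.

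The cost is a change to the allocation script, seven model degrees of freedom (three for hospital, four for round) and occasional 11/13 groups. Hospital must also be known for the whole round before it is allocated. In a round of exactly 24, the number of hospitals with odd counts is even, so dividing the extra nurses equally between the arms at random would keep 12/12; the permutation check should then follow the same rule. If the sponsor prefers not to stratify, adding the hospital term alone captures most of the gain where the gain is largest.

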#### **A. Outcome Measure(s):**

##### **Outcomes Variables:**

1. **The primary outcome** will be post-pre changes in the CD-RISC scores in intervention and control subjects.
2. **Acceptability** will be measured with the eight-item self-report Client Satisfaction Questionnaire (CSQ-8) 103, 138. The CSQ-8 is designed to yield a homogeneous estimate of general satisfaction. Scores range from 8 to 32 (higher scores indicating greater satisfaction). The CSQ-8 will be administered after the final treatment and control session.
3. **Adherence** will be measured for each component of the intervention and a total overall adherence will be calculated. Our research personnel will record study participant's attendance at each of the sessions and completion of assigned daily practices. Study participants will complete REDCap diary cards and record their weekly participation in out of class activities. Adherence will be calculated from these two sources of information. The total adherence will be calculated by adding each individual intervention component adherence divided by the total number of components.
4. **Additional outcomes:** Participants will also complete post-intervention MBI, PDS, and HADS surveys.
5. **Qualitative Interviews** will also be administered to provide an assessment of participant satisfaction with the intervention and control program. Interviews will be digitally audio recorded and transcribed for coding. Three questions specifically inquired about the helpfulness of the intervention and control programs: "Has the program been helpful to you?" "Has the program changed how you cope with work related stress?" and "Has the program changed how you cope with times when you feel you may start to become stressed at work?" Additional open-ended questions will be used to elicit participant descriptions of their program experience. These interviews will be audio recorded and transcribed as described in Aim 1.

#### **B. Description of Population to be Enrolled:**

We will enroll ICU nurses from four Colorado hospitals. From the beginning of our proposal preparation, all of the Chief Nursing Officers (CNOs) and ICU Nurse Managers have been involved in the study development. Uniformly, these CNOs are excited to have nurses from their hospital participate in the trial. Enrollment at diverse hospitals will help substantiate the generalizability of our findings. There are no studies at these hospitals that compete with this study enrollment.

##### **Inclusion Criteria:**

1. Male or female, ages 18+
2. Employed as a critical care nurse and work at least 20 hours per week as an ICU.
3. Baseline score of < 82 on the Connor-Davidson Resilience Scale (CD-RISC)

4. Positive symptoms of at least one BOS dimension using the Maslach Burnout Inventory (MBI): emotional exhaustion score of >17, depersonalization score of >7, or a personal accomplishment score of < 31

**Exclusion Criteria:**

1. A self-reported diagnosis of bipolar or psychotic disorder, active substance dependence, or immediate risk of self-harm or need for hospitalization
2. Unwillingness to participate in the entire study protocol
3. Employment on a time limited contract (i.e. a traveling nurse)

**C. Study Design and Research Methods**

**The MBCT resiliency program (MBCT-ICU):**

The MBCT-ICU will teach participants to remain aware of the present and not allow thoughts to become overpowering, especially in times of emotional upheaval. Participants will receive training in sitting, movement, speaking, listening, and compassion for others and self. They will learn how to apply these techniques to ICU nursing and everyday life. The MBCT-ICU intervention will be 16 in-person hours conducted in group sessions or 16 hours of mixed in-person and online intervention, using the MMB (insert program here, developed by [name] and [name]) and Skype/Zoom. New material is introduced through experiential exercises followed by group input and discussion. Participants in the program will also be asked to engage in a daily meditation practice and complete homework exercises to integrate the application of awareness skills into daily life. The first sessions are devoted to facilitating non-judgement awareness of the present experience. This is accomplished, in large part, via the formal meditation practices, that help participants to learn a number of important skills including concentration, awareness of thoughts, feelings, and bodily sensations as well as being in the present moment. Together, these skills facilitate the participants' ability to deconstruct their experience into the component elements of physical sensations and the accompanying thoughts and emotions. The second half of the program develops more flexible and deliberate responses at time of stress at work. Acceptance as a skillful step in dealing with one's work environment is explicitly explored. All participants will receive an audio file for home practice. The MBCT-ICU program will be taught by two instructors.

The in-person sessions will be video recorded for intervention fidelity purposes. The videos will be stored on a HIPAA compliant file that will only be shared with select study staff. The videos will be destroyed after the study concludes.

**Control Book Club Group:**

There will be one to two instructors, both trained in leading group discussions. 2-3 books will be chosen in advance, by the study team, to read during the intervention period.

**Homework Assignments:**

Your homework assignment will include reading daily for at least 25-30 minutes.

**D. Description, Risks and Justification of Procedures and Data Collection Tools:**

**Protection against risks of confidentiality:** Because we are collecting potentially sensitive/stigmatizing information, we will keep the data stored in an electronic format

(REDCap), and we will keep this information on a password protected and encrypted laptop and under lock and key. The office where the information will stay is a study staff only office.

There is the potential risk of breach of confidentiality related to subjects' responses to survey questions. This risk is minimized by using a unique subject ID instead of name when filling out surveys. RedCap will also be used for the survey responses, which further protects confidentiality by using a secure and encrypted environment. Since some subjects are nurses within the University system and the study team is faculty of the University system, an anonymous and confidential environment will help ensure disclosure by the participants.

**Protection against risks of mental health issues:** There is also a potential risk for identifying underlying mental health issues through the MBCT sessions, and the survey responses. For issues such as passive suicidal ideation or symptoms of depression, anxiety, or PTSD, an informational sheet will be provided with resources available for additional mental health services. Additionally, at the beginning of the program, all subjects will be informed that the training program may uncover unresolved and distressing thoughts or feelings; and a list of resources will also be provided at that time.

**Suicidality Response Plan:** We have developed a specific protocol if any study participant expresses suicidal thought at any point during the study. All study participants will be informed of this suicidality response plan prior to signing the informed consent for their participation in the study. We will require all of our personnel to complete the online Columbia Suicide Severity Rating Scale (C-SSRS) training. Training can be administered through a 30-minute interactive slide presentation followed by a question-answer session or using a DVD of the presentation. Those completing the training are certified to administer the C-SSRS, and will receive a training certificate. The training certificate is valid for two years. This scale can be used to delineate high, moderate, and low-risk levels. If the participant is deemed to be at high risk, then the PI or one of the co-investigators will be notified immediately. Using the C-SSRS, the PI will then help to assess the participant to determine if they endorse active suicidal ideations. The PI will also determine if the participant is currently being treated by a mental health professional.

If the patient is deemed to not be actively suicidal, then they will be given a list of local mental health resources. If the participant is considered to be actively suicidal then one of the following plans will be followed depending on the location of the participant 1. If the participant is with one of the study personal: a. The study personnel will notify [name] or one of the co-investigators immediately. b. Then the study personnel will either physically walk the subject to the emergency department, or call the Psychiatric Emergency services [contact]). Resources are available 24 hours a day, 7 days a week. 2. If the participant is on the telephone: a. The study personnel will notify [name] or one of the co-investigators immediately. b. The study personnel will stay on the telephone with the subject participant. c. The study personnel will immediately contact 911 to initiate an on-site rescue if such action is clinically indicated. d. The study personnel will stay on the telephone with the subject until EMS services have contacted the participant. 3. If there are any active suicidal concerns in any of the surveys or questionnaires: a. The study personnel will notify [name] or one of the co-investigators immediately. b. Next, the study personnel will contact the participant by telephone. c. The study personnel will stay on the telephone with the subject participant. d. The study personnel will use a different telephone line to immediately contact 911 to initiate an on-site rescue if action is clinically indicated. e. The study personnel will stay on the telephone with the subject until EMS services have contacted the participant. If the participant is determined to be actively suicidal and require immediate medical therapy, they will be withdrawn from the study.

### **E. Potential Scientific Problems:**

After the completion of each intervention and control cohorts, the research team will be convened to examine general trends and patterns in feedback from intervention and control participants and in the instructor's ratings across sessions. When necessary, this information will be used to revise the MBCT-ICU protocol. We did not include refresher sessions that are often offered every three months during the following year after the conclusion of other eight week MBCT courses 145. This decision was due to the time restrictions of an R34 mechanism

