#### **II. Aim 1: With stakeholder engagement, we will optimize our MBCT resiliency program for ICU nurses.**

#### **III. Aim 2: By conducting a randomized pilot clinical trial, we will:**

- a. Aim 2a: Refine the acceptability of the MBCT resiliency program and the control intervention.**
- b. Aim 2b: Identify the most feasible randomization level to minimize contamination between the control and intervention groups.**

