## **G. Summarize Knowledge to be Gained:**

By creating sustainable change in an ICU nurse's ability to adapt to their work environment, we anticipate that our MBCT-ICU program will enhance nursing performance in an extremely stressful job; decrease BOS symptoms; and allow nurses to more effectively care for patients in the challenging ICU environment. The results of this study will be used as preliminary data to support a larger clinical trial to determine the effectiveness of the intervention.

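### MBCT-ICU may be revised between rounds, but the primary comparison ignores round, version and delivery mode, so its average effect may not be that of the version carried forward

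*Combined protocol and SAP*

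**What the plan says.** Section IV (Methods/Randomization) runs the trial in successive rounds of about 24 nurses, each randomised 1:1 to 12 treatment and 12 control. The timetable is "5 treatment and 5 control cohorts x 2 month interventions = 10 months".

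Section E provides for review between rounds: "After the completion of each intervention and control cohorts, the research team will be convened to examine general trends and patterns in feedback". It continues: "When necessary, this information will be used to revise the MBCT-ICU protocol". No limit on revisions, freeze point or version log is given.

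Section C gives the programme as "16 in-person hours conducted in group sessions or 16 hours of mixed in-person and online intervention", without saying which form applies when. The book-club description gives no delivery mode.

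For the analysis, Section F states that "our primary outcome variable will be the post-pre change in CD-RISC scores in intervention and control subjects". It powers one comparison of arms on 160 subjects with an equal-variance t test and adds bootstrap and permutation checks. Round, version and mode do not appear in it.

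On use, Section G says: "The results of this study will be used as preliminary data to support a larger clinical trial".

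**The concern.** A comparison over all rounds estimates the mean of the round-specific effects. If the programme changes materially during the trial, that mean describes a mixture of versions. The larger trial will presumably test one settled version, most naturally the last, though the documents do not say so. The two quantities need not agree, and the plan keeps no record that would let a reader set them side by side.

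Two further consequences follow. Section F says that a failure to see the expected difference may be due to contamination. A weaker early version, or a weaker delivery mode, would be a rival explanation that could not be examined without a version and mode record. Also, Aim 2a is to "Refine the acceptability of the MBCT resiliency program and the control intervention", yet nothing commits the team to showing CSQ-8 or adherence by version, which is the natural display of whether refinement worked.

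**Working it through.** **Inputs.** From Section F: SD 20, difference 12 points, two-sided alpha 0.05, equal-variance t test, N = 160. From Section IV: five rounds, 12 per arm per round, so 5 × 24 = 120.

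**The plan's own power figure.** Exact t-test power for 12 points is 96.5% with 80 per arm (N = 160) and 90.3% with 60 per arm (N = 120). The stated 90% therefore matches the five-round total, not 160; at 24 per round, 160 would need 160/24 = 6.7 rounds. That mismatch is a separate matter and does not affect this point, but both totals are carried below.

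**What the all-rounds comparison estimates.** With equal rounds it is the simple mean of the round effects. The patterns below are assumptions, shown only to give a range:

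| Round effects (points) | All-rounds mean | Last round |
|---|---|---|
| 12, 12, 12, 12, 12 | 12 | 12 |
| 19, 12, 12, 12, 12 | 13.4 | 12 |
| 6, 6, 12, 12, 12 | 9.6 | 12 |
| 8, 10, 12, 14, 16 | 12 | 16 |
| 4, 8, 12, 16, 20 | 12 | 20 |

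The gap runs from nothing to 8 points, depending entirely on the assumed drift.

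**Precision by amount of data.** SE = 20 × sqrt(2/n) for n per arm; the 95% half-width is the t quantile on 2n − 2 degrees of freedom times the SE.

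| Data used | n per arm | SE | 95% half-width |
|---|---|---|---|
| One round | 12 | 8.16 | 16.9 |
| Two rounds | 24 | 5.77 | 11.6 |
| Three rounds | 36 | 4.71 | 9.4 |
| All, N = 120 | 60 | 3.65 | 7.2 |
| All, N = 160 | 80 | 3.16 | 6.2 |

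**Could drift be detected?** For a linear change in effect over five rounds coded −2 to 2, the sum of squares is 10, so the SE of the slope is 8.16/sqrt(10) = 2.58. Approximate power is Φ(slope/2.58 − 1.96): 12% for 2 points per round, 21% for 3 and 34% for 4. A formal test of drift would be uninformative.

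**Should the final-version figure replace the pooled one?** Suppose the programme changed once, after round 2.
- Final-version variance: 400 × 2/36 = 22.2.
- Pooled variance: 400 × 2/60 = 13.3.
- Pooled bias for the final version: 2/5 = 0.4 times the version difference d.
- The final-version estimate has the lower mean squared error only if 13.3 + 0.16d² > 22.2, that is, d above about 7.5 points.

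For smaller changes the pooled figure is the better guide.

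**Cost of a round term.** With 12 against 12 in every round, the stratified estimate equals the plain difference in means. Four round indicators take the residual degrees of freedom from 118 to 114.

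**The case against.** Refinement is a declared purpose of this pilot (Aim 2a), revision is conditional, and five versions is a ceiling; the changes might be small or none. Concurrent 1:1 allocation in each round means that neither bias nor type I error in testing an average effect is at issue. An average over an evolving programme is a legitimate pilot quantity. Section F writes out no primary model: the t test is a power assumption, and pooling is inferred from the single comparison on total enrolment. All of this stands.

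Four stronger readings are tempting, but the documents do not support them.

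- *CSQ-8 and adherence are pooled, so improvement cannot be seen.* Section A defines them and Section F gives no analysis for them; pooling is not stated. Feedback is reviewed after each cohort.
- *Delivery mode will vary between rounds.* Section C says one form or the other, in a sentence that still holds an unfilled placeholder. It may be an undecided choice.
- *The larger trial will be mis-sized by a calculable factor.* That needs an assumed drift and a larger trial sized on this CD-RISC estimate. Section G says only preliminary data, and item 12 of Section III links the power of the later trial to the contribution of burnout to turnover.
- *Each round gives a clean estimate for its version.* Each round has one group per arm, so a version effect is mixed with that group's own effect, and the half-widths above ignore this clustering.

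What the objection does not answer is that the analysis leaves out the rounds within which the trial randomises, and that no version or mode record is planned.

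**Conclusion.** The point holds as a gap in analysis and reporting, not as a validity error. The all-rounds comparison validly tests an average effect. It may differ from the effect of the version carried forward if revisions are material, and the plan has no means of showing whether it does. The documents give no size for the drift, so the effect patterns above are illustrations only.

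The precision figures rest on SD 20, equal rounds, complete data and no group clustering. One round gives about ±17 points, against about ±7 (N = 120) or ±6 (N = 160) overall. By-round and by-version results can therefore only be descriptive.

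A reader might infer that revisions must be confined to one point, or that the larger trial must be planned on the final-version figure alone. Neither follows. The first would restrict Aim 2a. The second gives the worse estimate unless versions differ by more than about 7.5 points in the case worked above.

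**What to change.** In Section F:
- Compare arms within round, with round as a stratum or fixed effect in the primary model, and permute within round so that the check follows the randomisation. Keep the all-rounds estimate as primary.
- Beside it, report the arm difference with its interval, CSQ-8 and adherence by round and by programme version and mode, including the rounds that used the final version. State that these are descriptive, that single-round intervals are about ±17 points, and that each round has one group per arm.
- For the larger trial, consider both the all-rounds and the final-version figures with their intervals.

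In Sections C and E: keep a dated log of version and delivery mode for each round. Where feasible, deliver the book club in the same mode as the MBCT group in that round.

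The cost is some wording, a log, a few extra table rows and four degrees of freedom with five rounds. Revision after each cohort can continue. The log should start before the next cohort, because it is hard to rebuild afterwards. Matching modes may need some scheduling effort.
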